dose, schedule, etc.)	
The PGx testing is comprised of Clinical Laboratory Improvement Amendments (CLIA) validated, panel-based genetic testing of two required genes, CYP2D6 and CYP2C19. The resulting CYP2D6 genotypes will be converted to enzymatic activity scores and the activity scores converted to metabolizer phenotypes after also taking strong and moderate CYP2D6 enzyme inhibitor drug interactions into account. The CYP2C19 genotypes will be converted to metabolizer phenotypes.
 
The results of the PGx test will be returned to the healthcare providers using standard site-specific laboratory return of results methods, a static report with both interpretation and recommendations, and where possible, interruptive clinical decision support (CDS) alerts within the electronic healthcare system. Both the static report and interruptive alerts will guide health care providers towards medications best suited to the participant.

Inclusion/Exclusion Criteria	
Inclusion Criteria:
 
Acute Pain
 
 • Age \geq 8 years • English speaking or Spanish speaking • Elective/planned surgery types with planned or anticipated to be treated with tramadol, hydrocodone, or codeine pain management at an enrolling site, which may include orthopedic surgeries (e.g. arthroplasty, spine, etc.), open abdominal surgery, or cardiothoracic surgery and others 
Chronic Pain
 
 • Age \geq 18 years • English speaking or Spanish speaking • Seen at primary care clinics (such as, but not limited to, Internal Medicine, Family Medicine or Pediatrics) or patients seen in pain-relevant specialty clinics • History of pain for at least the last 3 months • Currently treated or being considered for treatment with tramadol, hydrocodone, or codeine to improve pain management 
Depression
 
 • Age \geq 8 years • English speaking or Spanish speaking • Patients followed at psychiatry clinics or primary care clinics at an enrolling site (such as, but not limited to, Internal Medicine, Family Medicine, or Pediatrics) • Documentation of depression and/or provider report of depression • Evidence of depressive symptoms for at least 3 months based on patient interview or documentation in electronic health records • Recent initiation of SSRI therapy, recent revised SSRI therapy, or anticipated need for revised or new SSRI therapy per health care provider

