7.3 Follow-up Participant Assessments

The event that starts the post-intervention data collection timing are as follows.

Acute Pain:

- Date of surgery (intervention and control arms)

Chronic Pain and Depression:

- Intervention arm: When the pharmacogenetics results are returned to the provider and deposited in the EMR
- Control arm: At date of DNA sample collection plus one week, where one week reflects the average time from sample collection to returning the results to the EHR
- Note: There will be variability in time the results are returned to provider and when genotype-guided therapy is delivered to the participant, time from results being available to the next provider-participant interaction (e.g. email, clinic visit, new prescription order, phone visit, etc.) will be recorded by study personnel.

Post intervention assessment collection may be done by the University of Florida College of PharmacyCall Center. The center agents will be trained survey collectors*, using an IRB approved telephone script. The collected survey responses will be entered into the study database. If preferred, the participant will have the option to complete the study follow-up survey by a URL link sent by text (to mobile phone) or email and captured in REDCap database

In the event that the call center is unable to reach a participant, local study coordinators may contact participants to facilitate completion of the follow-up surveys.

Data will be collected in the following timeframes*:

- Acute pain: 10 days, 1 month, 3 months, and 6 months post-surgery
- Chronic pain and depression: 1-month, 3 months, and 6 months post return of results for the intervention arm, and post baseline assessments for the control arm.

*See *MOP for call center agents and survey collection interval windows*

All Trials

PROMIS 43 – Adults (≥ 18 years of age) will complete a 43-question survey assessing well-being and sub domains: pain interference, physical function, sleep disturbance, social role and activities functioning, fatigue, anxiety, and depression.[32] This survey will be administered to adult participants at baseline, 1-month, 3-months, and 6-months post-surgery (acute pain), or baseline, 1-month, 3-months, and 6-months post return of results (chronic pain, depression).

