PROMIS pediatrics 37 – Pediatric study participants (ages 8-17) will complete a 37-question survey assessing pediatric well-being and sub domains: pain interference, physical function, sleep disturbance, social role and activities functioning, fatigue, anxiety, and depression. This survey will be administered to pediatric participants at baseline, 1-month, 3-months, and 6-months post-surgery (acute pain), or baseline, 1 month, 3 months, and 6 months post return of results (depression).

Health care utilization – Survey of the number of significant cost driver health care encounters (e.g. hospitalizations, clinic visits, etc.). This survey will be administered to participants at 10-day, 1-month, 3-months, and 6-months post-surgery (acute pain), or baseline, 1-month, 3-months, and 6-months post return of results (chronic pain, depression).

Medications - Participant medications will be collected using patient surveys at baseline and the primary endpoint time points: 10-days for Acute Pain and 3-months for Depression and Chronic pain.

Productivity loss – Survey of loss of work the time and pay lost due to the participant's depression or pain. This survey will be administered to participants at 1-month, 3-months, and 6-months post-surgery (acute pain), or 1-month, 3-months, and 6-months post return of results (chronic pain, depression).

Acute Pain:

PROMIS Numeric Rating Scale - Pain Intensity - An 11-point numeric scale ranging from 0 (no pain) to 10 (worst possible pain) for average pain. This survey will be administered to all participants at baseline, 10 days, 1-month, 3-months, and 6-months post-surgery.

PROMIS pain intensity scale – A participant completed 3-question survey of average pain over the last 7 days, worst pain over the last 7 days, and current pain. Each question is on a 1-5 integer scale, the higher the value, the more intense the pain. This survey will be administered to all participants at baseline, 10 days, 1-month, 3-months, and 6-months post-surgery.

Opioid consumption questionnaire – A participant completed survey of pain prescription medication consumption, including the type of opioid pain medication, number of pills dispensed, if a refill has been obtained, and the number of pills left for each opioid pain medication selected. This survey will be administered to all participants at 10 days and 1-month post-surgery.

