7.5 Specimen Transfer and Genetic Testing Procedures

All collected specimens will be clearly marked with two patient identifiers (CLIA requirement). Samples from the Intervention arm participants will be processed, using analytically validated PGx testing procedures (see Table 1 for gene and variant list). For Control arm samples, designated laboratories will either extract DNA after sample receipt, and store the DNA for later analysis or store the sample and extract DNA after the Control participant has completed the 6-month follow-up assessment. After the Control participant has completed the 6-month follow-up assessment, Control Arm samples will be processed using analytically validated procedures. Details of sample storage and transport will be presented in the MOP.

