In the University of Florida's pilot acute pain study, the difference between study arms in SIA score was -38.55 with a SD of 93.5, for a standardized effect size of 0.412. Assuming a reduced standardized effect size of 0.375, 304 participants with an actionable phenotype per group, 152 from the intervention arm and 152 from control arm, are required to achieve 90% power for a two-sided two-sample t-test. Preliminary data from the University of Florida's acute pain study indicates the proportion of participants with an actionable phenotype, genotypic or pheno-converted CYP2D6 IM or PM, will be approximately 18%. After adjusting for the subset anticipated to have an actionable phenotype, 845 participants completing all assessments, per group, are required to achieve 90% power in the sub-group analysis (1678 total). Assuming 10% drop out or lost to follow-up and 7% of participants not going on to surgery, a total of 2020 randomized participants is required to sufficiently power this study. Factoring in variability in the proportion that are IMs or PMs (15% to 24%), 1516 to 2424 randomized subjects would be need to achieve 90% power in the mITT analysis.

Chronic Pain: In the University of Florida's prior chronic pain study, the difference between study arms in composite pain score was 0.6 with a SD of 1.4, for a standardized effect size of 0.43. The same effect size was observed when assessing 3-month changes in pain scores. Assuming a standardized effect size of 0.40, 268 participants within the specified subgroup, 134 from the intervention arm and 134 from control arm, are required to achieve 90% power for a two-sided two-sample t-test. Preliminary data indicate the proportion of participants with an actionable phenotype will be 30-35%; 10-15% of participants with an actionable genotype-based phenotype (CYP2D6 IM or PM) and an additional 20% with a pheno-converted PM/IM based on drug-drug-gene interactions. After adjusting for the subset anticipated to have an actionable phenotype, 447 participants completing all assessments, per group, are required to achieve 90% power in the sub-group analysis (894 total). Assuming 10% drop out or lost to follow-up, a total of 994 randomized participants is required to sufficiently power this study. Factoring in variability of the proportion of randomized population that are IMs or PMs (24-33%), 906 to 1244 randomized subjects would be need to achieve 90% power in the mITT analysis.

Depression:

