10.3 Population for Analyses

Acute pain

Participants randomized who have an actionable phenotype, specifically participants who are genotypically or pheno-converted CYP2D6 IM or PMs (i.e. CYP2D6 activity score ≤ 0.75).

Chronic pain

Participants randomized who have an actionable phenotype, specifically participants who are genotypically or pheno-converted CYP2D6 IM or PMs (i.e. CYP2D6 activity score ≤ 0.75).

Depression

Participants randomized who have an actionable phenotype, specifically participants who are genotypically or pheno-converted CYP2D6 PM or UMs or CYP2C19 PM, RM, or UMs.

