The primary analysis is a modified intent to treat design and the analytical subgroup is defined by the results of the PGx testing. Because the drug metabolizer phenotypes for participants in the Control arm is determined around the time of the 6-month follow up assessments for all trials (Acute Pain, Chronic Pain, and Depression), only participants that have completed their 6-month assessments will be included in the interim analysis. To account for the delays in receiving genetic testing results, the interim analysis will be targeted to occur when approximately 50% of the participants have completed their 6-month assessments. If the interim analysis does not propose stopping for efficacy (p-value <0.0003 and the intervention has the larger reduction in the primary endpoints), then the conditional power to detect a significant result at the end of the trial will be estimated. The conditional power will be presented to the DSMB to facilitate discussion of whether the trial should be stopped for futility.

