14.2 APPENDIX B. TABLE OF MINIMUM REQUIRED VARIANTS

Gene	Allele	Variant	dbSNP
CYP2C19	*2	681G>A	rs4244285
	*3	636G>A	rs4986893
	*4	1A>G	rs28399504
	*6	395G>A	rs72552267
	*8	358T>C	rs41291556
	*17 (also *4 haplotype [*4B])	-806C>T	rs12248560
CYP2D6	*2	2850C>T	rs16947
	*2	4180G>C	rs1135840
	*3	2549delA	rs35742686
	*4	1846G>A	rs3892097
	*5	CYP2D6 deleted	
	*6	1707delT	rs5030655
	*8	1758G>T	rs5030865(A)
	*9	2615_2617delAAG	rs5030656
	*10 (also *36 gene conversion)	100C>T	rs1065852
	*17	1023C>T	rs28371706
	*29 (also *70)	3183G>A	rs59421388
	*41	2988G>A	rs28371725
	1XN	copy number	
	2XN	copy number	
	4XN	copy number	
	9XN	copy number	
	17XN	copy number	
	29XN	copy number	

	41XN	copy number	
--	------	-------------	--

14.3 APPENDIX C. CYP2D6 INHIBITORS AS DEFINED BY THE FDA GUIDENCE ON DRUG INTERACTIONS

As of 3/6/20:

Strong Inhibitors	bupropion, fluoxetine, paroxetine, quinidine, terbinafine
Moderate Inhibitors	abiraterone, cinacalcet, duloxetine, lorcaserin, mirabegron

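### The plan sets no medication date for CYP2D6 pheno-conversion, so drugs started or stopped after randomisation could change who is in the primary set, and differently by arm

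*Combined protocol and SAP*

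**What the plan says.** **How phenotype is formed.** The synopsis says that genotypes become activity scores and "the activity scores converted to metabolizer phenotypes after also taking strong and moderate" CYP2D6 inhibitors into account. Section 7.1 gives the rule: a strong inhibitor makes the participant a poor metabolizer (PM), and a moderate one halves the activity score.

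**Who is in the primary set.** Section 10.3 counts pheno-converted participants in every trial. For depression the set is "specifically participants who are genotypically or pheno-converted CYP2D6 PM or UMs or CYP2C19 PM, RM, or UMs". For both pain trials it is genotypic or pheno-converted CYP2D6 intermediate metabolizers (IM) or PM.

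**When phenotype is known.** Section 7.5, on controls: "After the Control participant has completed the 6-month follow-up assessment, Control Arm samples will be processed using analytically validated procedures". Section 10.7, for all trials: "the drug metabolizer phenotypes for participants in the Control arm is determined around the time of the 6-month follow up assessments". For the intervention arm of the chronic pain and depression trials, Section 7.3 starts follow-up as follows: "Intervention arm: When the pharmacogenetics results are returned to the provider and deposited in the EMR". It gives one week as the average time from sampling to results.

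**Which drugs are inhibitors.** Appendix C (14.3) lists as strong "bupropion, fluoxetine, paroxetine, quinidine, terbinafine". Duloxetine is among the moderate ones.

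**Which medication records exist.** Section 7.2 collects baseline medications from the health record and/or self-report. Section 7.3 says "Participant medications will be collected using patient surveys at baseline and the primary endpoint time points". Section 7.8 extracts prescriptions from time zero to six months. None of these sections links a record to membership of the analysis set.

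**The concern.** Comparing two subsets of randomised arms is protected by randomisation only if the trait defining the subset is fixed beforehand. Genotype is such a trait, and so is CYP2C19 status as this plan defines it. CYP2D6 inhibitor use is not.

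Several of the listed inhibitors are also treatments that may be started or stopped because of the outcome. Bupropion, fluoxetine, paroxetine and duloxetine are antidepressants. Paroxetine is also a study drug on which Table 6 advises prescribers by phenotype, so the intervention itself can alter inhibitor exposure. If any list made after randomisation decides membership, membership can depend on treatment or response.

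An example of what the text permits, though it does not state it: a control with normal CYP2D6 and CYP2C19 phenotypes is moved to a strong inhibitor in month 2 and is classed at month 6 as a pheno-converted PM, so enters the set. The same person in the intervention arm, classed when results came back, would not be in it. Equally, a control who stops an inhibitor could leave the set. The primary estimate and type I error in each trial, and the interim analysis, rest on these sets.

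**Working it through.** **1. The plan's sample sizes reproduce.** Inputs from 10.1: two-sided two-sample t-test, alpha 0.049, power 90%, standardized effects 0.375, 0.40 and 0.28. The noncentral-t calculation gives 152, 134 and 271 per arm for acute pain, chronic pain and depression, as stated. The point concerns how the sets are formed, not their size.

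**2. Share exposed to the rule, chronic pain (the plan's own figures).** Section 10.1 expects 30-35% actionable: 10-15% by genotype and "an additional 20% with a pheno-converted PM/IM based on drug-drug-gene interactions".
- 20/35 = 57%; 20/30 = 67%.
- Of 268 participants: 268 × 20/35 = 153; 268 × 20/30 = 179.

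These participants qualify only through inhibitor use. A stable user is classed the same on any date, so this is not a misclassification rate. The split is not given for acute pain or depression.

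**3. Which inhibitors can move whom (Table 3 and the 7.1 rule).**
- Pain trials: a strong inhibitor moves anyone to PM. A moderate one moves a score of 1.5 to 1.5 × 0.5 = 0.75 (IM, in the set), but 2.0 to 1.0 (normal, not in the set).
- Depression: IM is not actionable, so a moderate inhibitor brings nobody in. It can take an ultra-rapid metabolizer out, for example 3 × 0.5 = 1.5. Entry is through strong inhibitors.

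**4. Illustration for depression.** From the plan: 40% actionable (A), 271 per arm, T-score SD 10, planned difference 2.8. Assumed, not in the documents: a share s = 5% to 15% of otherwise non-actionable controls starts a strong inhibitor and is counted; these controls improve 2 to 4 points less; nobody leaves the set.

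Late-entrant share of the control set: q = s(1 − A)/[A + s(1 − A)].
- s = 0.05: 0.03/0.43 = 7.0%
- s = 0.10: 0.06/0.46 = 13.0%
- s = 0.15: 0.09/0.49 = 18.4%

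Shift in the arm difference = q × deficit: from 0.070 × 2 = 0.14 to 0.184 × 4 = 0.73 points. The upper end is 0.73/2.8 = 26% of the planned difference.

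Standard error of the difference = 10 × √(2/271) = 0.859. Probability of rejecting with no true effect:

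| Shift (points) | Shift/SE | Type I error |
|---|---|---|
| 0 | 0 | 4.9% |
| 0.14 | 0.16 | 5.2% |
| 0.50 | 0.58 | 8.8% |
| 0.73 | 0.85 | 13.4% |

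**5. Illustration for chronic pain, either direction.** Assume that 5% to 20% of the control set enters late and differs by 0.2 to 0.6 SD. The bias is 0.05 × 0.2 = 0.01 to 0.20 × 0.6 = 0.12 SD. With 134 per arm, type I error is 5.0% to 16.4%. Power at 0.40 SD is 63% to 89% if the bias is towards the null and 92% to 99% if away from it.

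**The case against.** The strongest reply is that Section 10.7 is about genotyping, not drugs. It explains the wait by delays in genetic results and does not mention inhibitors, and Section 10.1 gives the same reason. Section 7.3 and Table 8 schedule no medication survey at month 6, and baseline medications are collected in both arms. On this reading the control genotype arrives at month 6 and is combined with baseline drugs.

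That is a fair reading and may be the intended one. A reader might infer from 10.7 that controls will be classed on their month-6 drugs. The documents do not say so. That the intervention arm's analysis phenotype is fixed at result return is also an inference, drawn from when results and interaction advice are issued. Section 10.2 places detailed plans in separate per-trial documents, and 7.2 defers medication detail to the manual of procedures. Neither was available, and either might set the date.

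A reader might also infer that the bias must favour genotype-guided care. That does not follow. Controls who stop an inhibitor leave the set, and someone switched in month 2 may have improved by month 3.

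The mechanism is weak for a 10-day post-surgical endpoint, because there is little reason for the outcome to drive antidepressant changes.

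The gap itself still stands. Section 10.7 speaks of phenotype, which the plan defines to include inhibitors. Records made after randomisation exist (the endpoint survey and the 7.8 extraction), and nothing excludes their use.

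**Conclusion.** The concern holds as an unclosed risk of selection bias in the primary sets. The medication date for pheno-conversion is unstated in both arms, and the literal text lets classification differ by arm. The documents do not establish that bias will occur, and its direction is uncertain. It is most plausible in depression, where strong inhibitors are themselves antidepressants, and weakest in acute pain.

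The only size that comes from the plan itself is the exposed share in chronic pain, 57% to 67%. The depression range (0.14 to 0.73 points, type I error about 5% to 13%) and the chronic pain range depend on assumed switching rates and outcome differences. They show what is possible, not what is expected. The matter is worth settling before unblinded data are seen, because a date chosen afterwards could not be defended as prespecified.

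**What to change.** **Section 10.3, all three trials and both arms.** Define the analysis-set phenotype as the genotype activity score (Tables 2 and 3) adjusted only for CYP2D6 inhibitors in use at or before the randomisation date, taken from the baseline self-report and/or health record (7.2). State that later starts or stops do not change membership, whenever the sample is tested, and that classification is done blind to arm and outcome. For acute pain, use medications dated at randomisation, because 7.2 requires the baseline survey only before surgery.

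**Section 10.7.** Say that only the control genotype becomes available at about six months.

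**Sensitivity analysis.** Repeat each primary comparison in the set defined by genotype alone.

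**Cost.** Mainly wording, plus reclassification from data largely collected already. No sample size changes. Where the 7.2 record is undated or was taken after randomisation, sites would need to retrieve the medication list at randomisation, since the 7.8 extraction starts at time zero. Participants whose inhibitor use changes between randomisation and surgery or prescribing are classed by their earlier status, which may differ from the phenotype shown to the provider. In acute pain that interval can be long, because 6.3 allows up to 12 months from enrolment to surgery. The change concerns the analysis set only and leaves care and prescribing advice as they are.

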10. STATISTICAL ANALYSIS PLAN AND SAMPLE SIZE

10.1 Sample Size Determination

All trials power analyses are based on a modified intent to treat analysis, comparing the subset of intervention participants with have an actionable phenotype to the subset of control participants with an actionable phenotype. Effect sizes used to estimate power are based on prior studies of pain and depression pharmacogenetic testing and described below for each trial and shown in Table 8. Several steps were taken to generate a conservative sample size estimate. First, the power requirement was set to 90%. Second, sample sizes are adjusted for a 10% drop-out (for which UF has data from several studies that this is a good estimate). Third, slightly smaller effect sizes than what was observed in prior studies was used. Finally, sample size calculations are based on an alpha of 0.049, to allow one interim analysis with an alpha of 0.001 in each study.

Due to the study design and the delay in the control arm to obtaining the genotyping results required determine the actionable phenotype subgroup assignment, it is not feasible to directly monitor the number of randomized participants in the actionable subgroup for the enrollment stopping rule. Alternatively, the observed trial specific actionable phenotype percentages and the corresponding trial specific total enrollment targets will be used to identify when enrollment can conclude for a fully powered mITT study.

Acute Pain

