10.7 Interim Analyses

A single specified interim analysis is planned for each trial. To account for repeated significance testing of the accumulating data, the group sequential method of Lan and DeMets will be used as a guide for

interpreting this interim analysis. Monitoring boundaries for the primary endpoint will be based on a two-sided symmetric O'Brien-Fleming type spending function with an overall two-sided significance level of $\alpha=0.05$. The O'Brien-Fleming approach requires large critical values early in the study but relaxes (i.e., decreases) the critical value as the trial progresses.

Acute Pain

The interim analysis of the acute pain primary endpoint will compare SIA scores at 10 days post-surgery among participants with *CYP2D6* IM or PM phenotypes in the Control arm to participants with *CYP2D6* IM or PM phenotypes in the intervention arm.

Chronic Pain

The interim analysis of the chronic pain primary endpoint, pain control at 3 months post return of PGx testing result to providers, will be compared between the participants with *CYP2D6* IM or PM phenotypes in the Control arm and the participants with *CYP2D6* IM or PM phenotypes in the intervention arm.

Depression

The interim analysis of the depression primary endpoint, depression control at 3 months post return of PGx testing result to providers, will compare the participants with *CYP2D6* PM/UM or *CYP2C19* PM, RM and UM phenotypes in the Control arm to the participants with *CYP2D6* PM/UM or *CYP2C19* PM/RM/UM phenotypes in the intervention arm.

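### The interim efficacy threshold of p<0.0003 is not the O'Brien-Fleming boundary the plan adopts (p<0.003 at 50% information), and the sample-size section gives a third value, 0.001

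*Combined protocol and SAP*

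**What the plan says.** Section 10.7 (Interim Analyses) fixes four things. There is one look: "A single specified interim analysis is planned for each trial". The method is Lan-DeMets, used as a guide: "Monitoring boundaries for the primary endpoint will be based on a two-sided symmetric" O'Brien-Fleming-type spending function, with an overall two-sided level of 0.05. On timing, "the interim analysis will be targeted to occur when approximately 50% of the participants have completed their 6-month assessments". The rule itself is "stopping for efficacy (p-value <0.0003 and the intervention has the larger reduction in the primary endpoints"; if it is not met, conditional power is calculated and shown to the DSMB for a discussion of futility.

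Section 10.1 (Sample Size Determination) states the levels differently: "sample size calculations are based on an alpha of 0.049, to allow one interim analysis with an alpha of 0.001 in each study". The final level of 0.049 is repeated for all three primary tests in the synopsis and in section 10.4.

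**The concern.** A spending function, an overall alpha and an information fraction together determine the interim boundary, so nothing is left to choose. The plan gives all three and then prints a number that does not follow from them, while section 10.1 prints another. A DSMB working from this text would face three rules:

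| Interim p | Boundary from stated method | 0.001 (section 10.1) | 0.0003 (section 10.7) |
|---|---|---|---|
| 0.0005 | crosses | crosses | does not cross |
| 0.002 | crosses | does not cross | does not cross |

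The same ambiguity applies in all three trials. It carries into the futility step, because conditional power is calculated only when the efficacy rule is not met.

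**Working it through.** **Inputs.** From section 10.7: overall two-sided alpha 0.05, O'Brien-Fleming-type spending, one look, t = 0.50. From section 10.1: final alpha 0.049, power 90%, and effect size with number per arm of 0.375 and 152 (acute pain), 0.40 and 134 (chronic pain), 0.28 and 271 (depression).

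**Sample sizes reproduce.** The exact two-sample t-test at alpha 0.049 and 90% power needs 151.2, 133.0 and 270.4 per arm, against the stated 152, 134 and 271. The final 0.049 is therefore the level actually used.

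**Interim boundary.** The two-sided symmetric form is α(t) = 4[1 − Φ(z₀.₉₈₇₅/√t)], with z₀.₉₈₇₅ = 2.2414. At t = 0.50:

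- 2.2414/√0.5 = 3.170
- 1 − Φ(3.170) = 0.000763
- 4 × 0.000763 = 0.00305, so |Z| ≥ 2.963

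**Final level.** The two test statistics have correlation √0.5. Setting the total two-sided crossing probability to 0.05 gives a final critical value of 1.969, which is p = 0.0490. This is the plan's own figure.

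**Where the printed values would belong.** The function equals 0.0003 at t = 0.350 and 0.001 at t = 0.415. For t from 0.45 to 0.55 it runs from 0.0017 to 0.0050, so approximate timing does not reach either value.

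**Other readings at t = 0.50.** None gives 0.0003:

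| Reading | Interim p |
|---|---|
| One-sided p | 0.00153 |
| Overall alpha 0.049 | 0.00294 |
| Overall alpha 0.025 | 0.00082 |
| Single-tail form, 2[1 − Φ(z₀.₉₇₅/√t)] | 0.0056 |
| Classical two-look O'Brien-Fleming | 0.0052 |

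**Consequences.** The chance of crossing under the design effect is 1 − Φ(z₁ − d·√(n/2)·√0.5). The drift term d·√(n/2)·√0.5 is 2.312 (acute pain), 2.315 (chronic pain) and 2.305 (depression).

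| Interim p | z₁ | Final level that uses up 0.05 | Overall alpha if final is 0.049 | Chance of crossing: acute / chronic / depression |
|---|---|---|---|---|
| 0.0003 | 3.615 | 0.04996 | 0.0490 | 9.6% / 9.7% / 9.5% |
| 0.001 | 3.291 | 0.0498 | 0.0492 | 16.4% / 16.5% / 16.2% |
| 0.00305 | 2.963 | 0.0490 | 0.0500 | 25.8% / 25.9% / 25.5% |

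In depression, half information is 135.5 per arm, so the standard error of the standardized difference is √(2/135.5) = 0.1215. The observed effect needed is 3.615 × 0.1215 = 0.44 SD under 0.0003, against 2.963 × 0.1215 = 0.36 SD under 0.00305.

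The only other route to 0.049 is the plain sum 0.001 + 0.049 = 0.05. That is an additive split, not O'Brien-Fleming spending, and it still disagrees with 0.0003.

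**The case against.** The arithmetic is not in dispute. The case on the other side is about weight.

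- **No false-positive risk, little power lost.** The printed threshold is the stricter one. With the final test at 0.049, overall alpha is 0.0490 and power is essentially the same under 0.0003 and 0.00305: 90.3% and 90.4% in acute pain, 90.4% and 90.5% in chronic pain, 90.2% under both in depression. This stands. The unspent alpha of 0.001 is minor, and no primary conclusion is biased.
- **The method is only a guide, and a separate DSMB SAP is foreseen in section 8.3.** Judgment around a boundary is normal, but it does not explain two different printed boundaries. The DSMB SAP is not among the documents, so it cannot be assumed to settle the matter.
- **Half the participants may not be half the information.** Control samples are genotyped only after the 6-month visit, so the phenotyped subset could lag. This is a fair limit on any fixed number, including 0.0031. But reaching 0.0003 would need information of about 35% against a target of 50%.
- **The 0.001 is sample-size wording, not a stopping rule.** It enters no calculation of n, so it is the weaker part of the conflict. It is still described as the alpha of the interim analysis and differs more than threefold from section 10.7.
- **A stricter interim could be deliberate.** That would be legitimate, but the plan does not say so and attributes its boundaries to O'Brien-Fleming spending. A dropped digit (0.003) is plausible but unconfirmed.

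**Conclusion.** The point holds. Under the method and timing in section 10.7 the interim boundary is two-sided p = 0.00305, not 0.0003 and not 0.001, and of the three only 0.00305 pairs with the final 0.049 under that method. The efficacy threshold as written is wrong by a factor of ten. The cost is an ambiguous stopping rule in three trials and a drop in the chance of crossing at the interim from about 26% to 10% if the design effects are true. It does not inflate type I error or materially change power. The figures assume 1:1 allocation in the actionable subset, normally distributed test statistics, and an information fraction of 0.50, which requires a stable share of actionable phenotypes among participants who have completed 6 months.

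**What to change.** In section 10.7, replace the fixed 0.0003 with the O'Brien-Fleming-type spending boundary evaluated at the actual information fraction in the phenotyped modified intent-to-treat subset. Give the 50% value as illustration (two-sided p<0.0031, |Z|>2.963) and state that the final level is recomputed from the same function (0.0490 at 50%). In section 10.1, replace the interim alpha of 0.001 with the same value. Carry the same text into the DSMB SAP. If a stricter interim level is intended, the plan should say so, name the rule that produces it, and give the matching final level.

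The cost is two sentences in the protocol and SAP plus the DSMB SAP; sample sizes and trial conduct do not change. The documents do not show whether any interim has already taken place. If one has, the boundary that was applied should be recorded.
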